9.7.3.3 Relationship Between Parameters

The changes from baseline for parameters (will be plotted against one another for Week 24 and Week 48 data. Week 24 and Week 48 data will be identifiable using different symbols. The Pearson correlation coefficients (for each week) will also be presented in the footnote of the plots.

9.7.4 Blood Biomarkers

All analyses will be performed on the Blood Biomarker population.

Biomarkers will be summarized by visit, along with their changes from baseline.

A decision was made to cease collecting MMP9, FGF19 and C4 after Week 48. Consequently, these data will only be summarized up to the Week 48 visit. Any data collected from subjects after Week 48 will be included in the listing.

9.8 Safety Analyses

9.8.1 Adverse Events

All safety analyses will be performed on the Safety population.

The listing of AEs will include the duration of the AE. It will be flagged if this is derived using imputed dates.

An overall summary will present the number (%) of subjects with:

- any TEAE

- any TEAE considered as related to study drug
- any serious TEAE
- Maximum intensity TEAE of none, mild, moderate, severe ; i.e. a subject with TEAEs at different intensities will be summarized at the most severe intensity
- any TEAE leading to study drug discontinuation
- any TEAE leading to death

The table will also include the total number of TEAEs reported and the total number of unique terms. For unique terms a preferred term will only be counted once within a subject.

Subject incidence of the following AEs will be tabulated by SOC (descending order of frequency) and PT (descending order of frequency):

- TEAEs
- treatment-related TEAEs
- maximum severity of TEAEs

Subject incidence of the following AEs will be tabulated by PT in descending order of frequency:

- TEAEs
- treatment-related AEs

Separate summaries will be generated for the first 24 weeks, first 48 weeks and for the whole study.

Serious TEAEs and TEAEs leading to discontinuation of study drug will be provided in by-subject listings.

Subjects will be counted only once within each SOC or PT. For tables categorized by severity, subjects with multiple events within a particular SOC or PT will be counted under the category of their most severe event for that SOC or PT.

9.8.2 Deaths and Serious Adverse Events

Subject listings of serious TEAEs, including treatment-emergent fatal AEs, will be provided.

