been limited to 14 days whilst that for F6 formulation 1 g *bid* dose level has been limited to 7 days. Neither has been associated with any safety signals except the observation of pale stools with both formulations and transient elevations in LFTs for the F6 formulation. The pharmacokinetics of SMT C1100 parent and metabolites, and the safety data, will be reviewed on an ongoing basis by the Sponsor and the data monitoring committee (DMC). As this is an open-label study, the Investigator should determine if an SAE is related to IMP and consider modifying the dose given. Serious AEs considered at least possibly related to IMP may require a dose reduction, a temporary hold or permanent discontinuation, with prior consultation and agreement with the Sponsor.

A risk relating to the study design is the requirement for the paediatric patients enrolled in this study to undergo up to two muscle biopsies, which will include the use of anaesthesia. This procedure may cause some discomfort but will be done with the assent of the patient, consent of their parents (or other adult legally responsible for them) and in a sensitive way that takes into account their age. The procedure will be explained to the patients in advance in an age appropriate manner and they and their parents will be given an opportunity to ask any questions they have relating to the procedure. Appropriate pain-relief will be made available following each biopsy.

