3.1. Primary Endpoints

- Change from baseline to Weeks 12, 24, 36 and 48 in MRI leg muscle parameters (Cohorts 1 and 2)
- SMT C1100 and metabolite plasma concentrations at Weeks 1 (Days 1 and 7, as applicable (Cohorts 2 and 3 only)), 4, 8 (Cohorts 1 and 2 only), 12, 24, 36 and 48
- Safety data including:
 - Treatment emergent AEs

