11.2. Serious Adverse Events

A serious AE (SAE) is any untoward medical occurrence that at any dose:

- Results in death
- Is life-threatening
- Requires inpatient hospitalisation or prolongation of existing hospitalisation
- Results in persistent or significant disability/incapacity
- or
- Is a congenital anomaly/birth defect

Medical and scientific judgment should be exercised in deciding whether reporting is appropriate in other situations, such as important medical events that may not reach the above definition but may jeopardise the patient or may require medical or surgical intervention to prevent one of the other outcomes listed in the above definition. These should also be considered serious. Examples of such events are invasive or malignant cancers, intensive treatment in an accident and emergency department or at home for allergic bronchospasm, blood dyscrasias or convulsions that do not result in hospitalisation, or development of drug dependency or drug abuse.

Serious AEs will be recorded from the signing of the consent form until the end of the safety follow-up period.

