12.1. Data Analysis Considerations

12.1.1. Analysis Populations

The ‘Safety’ and ‘Intent-To-Treat (ITT)’ populations will both be defined as all patients who receive at least one dose of study medication.

Separate populations will be identified for MRI and functional activity endpoints, based upon their baseline ability to be assessed for the relevant endpoint. Further information on these populations will be provided in the Statistical Analysis Plan.

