12.1.4.3. Safety Analyses

Adverse events will be summarised by system organ class and preferred term using the Medical Dictionary for Regulatory Activities. The frequency and percentage of patients will be tabulated for each of the following:

- All causality AEs
- Treatment-related (possibly or likely related to study drug) AEs
- Intensity (mild/moderate/severe) of AEs
- Serious AEs
- Adverse events leading to study drug discontinuation

Changes from baseline in laboratory assessments, vital signs measurements, pulmonary function parameters (including FEV and FVC) and ECG parameters will be summarised.

The relationship between safety endpoints and SMT C1100 parent and metabolite exposure may also be investigated.

Study Number: SMT C11005 Protocol	Compound No.: SMT C1100 Version: 5.0 24Feb2017
---	---

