5.4 Safety Assessments

5.4.1 Adverse Events (AE)

A treatment emergent AE (TEAE) includes any condition that: 1) was not present prior to study treatment, but appeared or reappeared following initiation of study treatment, or 2) was present prior to study treatment, but worsened during study treatment.

The duration of AEs will be derived as the AE end date (imputed date for incomplete AE end date) – AE onset date (imputed date for incomplete AE onset date) +1.

AEs leading to discontinuation of IMP are those with an action taken with study treatment on the AE eCRF page of “Drug Withdrawn”.

Treatment-related TEAEs are defined as those TEAEs where relationship to study treatment is either considered as ‘Possibly Related’ or ‘Probably Related’ by the Investigator. A missing value for relationship to treatment will be considered as ‘Related’ in summaries.

A missing assessment of severity will be considered as ‘severe’ in summaries.

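### The SAP counts and lists only treatment-emergent serious AEs, so a serious complication of the pre-dose biopsy would be missing from the SAE count and the SAE listing, and the SAP does not declare this narrowing

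*SAP*

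**What the plan says.** **Protocol.** Section 11.2 sets the recording window: "Serious AEs will be recorded from the signing of the consent form until the end of the safety follow-up period". Section 12.1.4.3 says that AEs will be summarised by SOC and PT, and continues: "The frequency and percentage of patients will be tabulated for each of the following". Five categories follow, and serious AEs are one of them. None is limited to treatment-emergent events. Section 1.3.4 states: "A risk relating to the study design is the requirement for the paediatric patients enrolled in this study to undergo up to two muscle biopsies". Section 6.2.1 allows local or general anaesthetic. Section 4.1.1 places one of the two biopsies at baseline.

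**SAP.** Section 5.4.1 defines a treatment-emergent AE (TEAE) as a condition that "was not present prior to study treatment, but appeared or reappeared following initiation of study treatment", or one already present that worsened on treatment. Section 9.8.1 says: "All safety analyses will be performed on the Safety population". For serious events, its overall summary has one line, the number of subjects with a serious TEAE. Its SOC/PT tables cover all TEAEs, treatment-related TEAEs and maximum severity, but not serious events. Section 9.8.2, on deaths and serious AEs, consists of one sentence: "Subject listings of serious TEAEs, including treatment-emergent fatal AEs, will be provided". Section 10 lists changes from the protocol's analyses and does not mention this one.

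**The concern.** The protocol's commitment on serious AEs starts at consent, while the SAP's starts at first dose. In many drug trials little of note happens between the two. Here an invasive procedure under anaesthetic takes place in that interval, in children, for study purposes, and the protocol itself names it as a design risk. The SAP already treats the biopsy as a distinct exposure in one respect: Section 9.4.2 puts the anaesthetic medications for it in their own listing. It has no matching provision for a serious event that follows the baseline procedure.

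What is at stake is the completeness of the SAE reporting. A reader of the study report who goes to the SAE count and the SAE listing would take them to cover the recording window in the protocol. They would cover only part of it, and nothing in the SAP says so.

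**Working it through.** **1. How many biopsies precede dosing.** Inputs are from Protocol 4.1.1 and 6.2.1.

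- Boys biopsied: about 30 (Cohort 1) + about 10 (Cohort 2) = 40. This matches the forty in the protocol summary. Cohort 3 has no biopsies.
- Baseline biopsies: 40.
- Second biopsies, Cohort 1: the first 8 boys at Week 24, then 22 assigned alternately, 11 to each time. That gives 8 + 11 = 19 at Week 24 and 11 at Week 48.
- Second biopsies, Cohort 2: 6 at Week 24 and 4 at Week 48.
- Second biopsies in total: (19 + 6) + (11 + 4) = 25 + 15 = 40.
- Pre-dose share: 40 / (40 + 40) = 50%.

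If a fraction d of boys has no second biopsy, the share is 40 / (40 + 40(1 − d)). For assumed values d = 5%, 10% and 20% this is 40/78 = 51.3%, 40/76 = 52.6% and 40/72 = 55.6%. Missed second biopsies can therefore only raise the share above one half.

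**2. Where a serious biopsy event would be reported.** Take one serious complication and apply the SAP rules to it.

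| Onset and course | Serious-TEAE count (9.8.1) | SAE listing (9.8.2) | General AE listing (9.8.1, with 9.1) |
|---|---|---|---|
| Week 24 or 48 biopsy | Yes | Yes | Yes |
| Baseline biopsy, worsens on treatment | Yes (5.4.1) | Yes | Yes |
| Baseline biopsy, onset not provably before first dose | Yes (9.1.1) | Yes | Yes |
| Baseline biopsy, onset before first dose, no worsening, boy later dosed | No | No | Yes, with a negative study day (5.1) |
| Baseline biopsy, boy never dosed | No | No | Not assured: outside the Safety population, and the Screened population is for disposition only (6.1) |

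The gap is the last two rows.

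**3. What fuller coverage is worth (illustration only).** With no serious biopsy events at all, the one-sided 95% upper bound on the risk per biopsy is 1 − 0.05^(1/n). For n = 40 it is 7.2%, and for n = 80 it is 3.7%. This treats a boy's two biopsies as independent. It shows how much less an empty SAE listing says when it covers only the post-dose half of the procedures.

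**4. Is the change declared?** SAP Section 10 gives four changes from the protocol: data access, the exposure measure, keeping Cohort 3 efficacy separate, and details deferred to a later version. Limiting serious AEs to treatment-emergent ones is not among them.

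**The case against.** There is a good case that the SAP is conventional here. The protocol's primary safety endpoint is "Treatment emergent AEs", and TEAE tables are the right tool for drug effects. In Protocol 12.1.4.3, the all-causality category can be read as the contrast to treatment-related AEs rather than as a promise to tabulate pre-dose events. SOC/PT and the list of categories also stand in separate sentences, so whether each category needs its own SOC/PT table is a matter of reading. These points justify keeping the TEAE tables. They do not explain why the listing of serious AEs starts later than the protocol's recording window, or why Section 10 is silent.

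A reader might go on to infer four stronger things that the documents do not support.

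- *That pre-dose harms vanish from the report.* They do not for dosed boys: SAP 9.8.1 plans an AE listing that is not limited to TEAEs, and 9.1 says that all data are listed. SAEs also reach the sponsor within 24 hours (Protocol 11.2.2), and the DMC reviews safety.
- *That the SAP dropped never-dosed boys against the protocol.* In Protocol 12.1.1 the Safety and ITT "populations will both be defined as all patients who receive at least one dose of study medication", so that limit is the protocol's own. Protocol 10.4 also restricts the data kept on screen failures.
- *That a treatment comparison is biased.* There is no control arm, and every boy in Cohorts 1 and 2 is planned to have one biopsy before dosing and one after.
- *That AEs leading to discontinuation are lost in the same way.* SAP 5.4.1 defines these by withdrawal of the drug, so an event that began before dosing and did not worsen will seldom qualify.

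Nor do the documents give a rate of serious biopsy complications, so no probability of such an event can be stated. Protocol 1.3.5 reports no SAEs in this study up to 7 February 2017, without saying how many boys had been biopsied by then.

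**Conclusion.** The point holds as a gap in SAE reporting. The SAP narrows serious AEs to treatment-emergent ones and gives no SOC/PT table for them. Protocol 11.2 and 12.1.4.3 set no such limit, and the change is undeclared. The events affected are serious complications of the baseline biopsy with onset provably before the first dose and no worsening on treatment. The procedures affected are about 40 of 80 planned, or 50%, and more if second biopsies are missed. This count assumes full enrolment in Cohorts 1 and 2 and two biopsies per boy.

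The consequence is limited. Conclusions on drug safety, MRI and function do not change, and the data for dosed boys remain in a listing. The change is worth making because it is cheap and concerns a procedural risk to children that the protocol names.

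**What to change.** 1. **SAP 9.8.2:** list all SAEs from consent, each flagged as pre-dose or treatment-emergent. Include any SAE recorded for a consented boy who was never dosed.
2. **SAP 9.8.1:** add the number of subjects with any SAE from consent, showing pre-dose and treatment-emergent events separately.
3. **SAP 9.8.1:** add a SOC/PT table of serious AEs, in line with Protocol 12.1.4.3.
4. Leave the TEAE tables unchanged.

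A separate table of all AEs following each biopsy is not proposed. Neither document gives a time window or a rule for attributing events to the biopsy, and without them such a table would mix procedure, drug and disease events.

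The cost is a few lines of SAP text and a small amount of extra output. For dosed boys the data are already collected. For never-dosed boys the listing can hold only what was recorded.

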9.8.3 Laboratory Data

Descriptive summaries of absolute values and changes from baseline will be provided for numerical laboratory parameters for each visit. At each visit the number of subjects with 'High', 'Low' or 'Normal' with respect to their reference range will be tabulated.

The categorical lab results will only be listed.

The number (%) of subjects who fulfill the following liver function test criteria at any time after the start of dosing will be tabulated:

- ALT \geq ULN, $\geq 2 \times$ ULN, $\geq 3 \times$ ULN
- AST \geq ULN, $\geq 2 \times$ ULN, $\geq 3 \times$ ULN
- Total Bilirubin \geq ULN, $\geq 2 \times$ ULN
- alkaline phosphatase $\geq 1.5 \times$ ULN
- GLDH \geq ULN

The number (%) of subjects who fulfill Hy's Law (ALT or AST $> 3 \times$ ULN + bilirubin $> 2 \times$ ULN, Alkaline Phosphatase must also be \leq ULN) will also be tabulated.

Separate summaries will be generated for the first 24 weeks, first 48 weeks and for the whole study.

These parameters will be listed, along with the value related to ULN (i.e. value/ULN) for subjects who fulfill one of the following criteria:

- ALT $\geq 2 \times$ ULN
- AST $\geq 2 \times$ ULN
- Total Bilirubin $\geq 2 \times$ ULN
- alkaline phosphatase $\geq 1.5 \times$ ULN
- GLDH \geq ULN

For each liver function test (ALT, AST, total bilirubin, alkaline phosphatase, GLDH) and creatine kinase, the value related to ULN (i.e. value/ULN) will be plotted against time in trellis plots, where each subject will have their own plot and the legend distinguishing the laboratory parameter. The plot will use a log10 scale with the axis labels reflecting the actual value (e.g. 1, 10, 100...).

For Cohort 2 the number (%) of subjects who fulfill the following coagulation test criteria at any time after the start of dosing will be tabulated:

- International Normalised Ratio $\geq 1.5 \times$ ULN
- Activate Partial Thromboplastin $>$ ULN

Separate summaries will be generated for the first 24 weeks, first 48 weeks and for the whole study.

A listing will also present all data that meet these criteria along with the value related to ULN (i.e. value/ULN).

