1.3.4. Risk Mitigation in Study SMT C11005

Three potential drug-related risks have been identified. One related to inhibition of the hERG channel by DHD I and DHD III, one related to potential interactions with concomitant medications, and one related to liver function test changes seen with F6.

The major metabolites of SMT C1100, DHD I and DHD III, caused between 25–45% inhibition of the hERG and human voltage-dependent calcium channel hCa_v1.2 at 30 µM. The highest individual plasma concentrations seen in patients dosed with F3 or F6 was at least 54-fold or 22-fold, respectively, below 30 µm for free DHD I and DHD III, and thus unlikely to cause QTc prolongation. However as a precaution and as this patient population is known to have significant ECG abnormalities and conduction defects, in this current and in previous clinical studies with patients with DMD, ECGs are being assessed frequently.

The preclinical pharmacokinetic studies indicated that SMT C1100 was primarily metabolized by CYP1A1 and CYP1A2. It was also shown that SMT C1100 could inhibit CYP1A1 and CYP1A2 in vitro; however, this inhibition was determined not to be clinically significant based on PBPK/Simcyp modelling (Study No. N-135). The metabolites of SMT C1100, DHD I and DHD III, were shown to induce CYP2B6. Based on the above, medication that induce CYP1A1 and/or CYP1A2 are restricted as are substrates of CYP2B6.

Study Number: SMT C11005	Compound No.: SMT C1100
Protocol	Version: 5.0 24Feb2017

SMT C1100, DHD I, and DHD III inhibited BCRP in vitro so given the role of this transporter in drug disposition and distribution, BCRP substrates are being excluded. DHD I and DHD III also inhibited OATP1B1 and OATP1B3 hepatic uptake transporters which could alter efficacy and increase the risk of exposure-dependent side effects of OATP1B1 and OATP1B3 substrates. Therefore, patients taking medications that are OATP1B1/1B3 substrates should be monitored for exaggerated pharmacological effects and exposure-dependent side effects as dose reduction may be needed. OATP1B1/1B3 substrates fluvastatin and rosuvastatin are also BCRP substrates and therefore excluded. Further details are provided in Section 9.2.

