Abnormal liver function tests were seen in patients with DMD dosed with the F6 formulation in the SMT C11004 study. AST and ALT are enzymes already raised in patients with DMD (although the likely source is muscle) and, as such, further elevations in these enzymes due to liver toxicity may be difficult to see. GLDH is being evaluated and is considered a more specific liver enzyme marker [Schomaker *et al*, 2013]. In addition, liver disease is characterised by reduced synthesis of the procoagulant proteins II, VII, IX, X, as well as factor V and factor XI. These factor deficiencies directly affect the standard coagulation measures available in clinical laboratories, mainly the prothrombin time (PT) and its standardisation, the international normalised ratio (INR), and to a lesser extent, the activated partial thromboplastin time (aPTT) [Northup and Caldwell, 2013]. Therefore, as a precaution and as a means to monitor liver dysfunction both GLDH and coagulation times will be measured.

Finally, during the SMT C11004 study stopping criteria based on liver function were developed. These are outlined below and will be followed during this study, as applicable.

If a patient's results meet either of the criteria below, dosing should be stopped and the tests should be repeated as soon as possible. If the repeated results still meet this criterion, the study drug will be permanently stopped and may not be restarted although the patient will continue to be followed for functional and MRI assessments for the duration of the study. If the patient is withdrawn from the study, a follow up visit should be arranged:

GLDH \geq 3x upper limit of normal (ULN)

OR

Bilirubin \geq 2x ULN together with an INR \geq 1.5x ULN (Cohort 2 and 3 only)

Patients in this study will receive either SMT C1100 2.5 g *bid* F3 formulation (Cohort 1 and Cohort 3) or SMT C1100 1 g *bid* F6 formulation (Cohort 2) for 48 weeks. Previous exposure at the F3 formulation 2.5 g *bid* dose level in the paediatric DMD population has

Study Number: SMT C11005	Compound No.: SMT C1100
Protocol	Version: 5.0 24Feb2017

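### SAP 9.8.3 criteria tables count neither of the protocol's two liver criteria, and the coagulation-criteria count leaves out Cohort 3

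*SAP*

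**What the plan says.** Protocol 1.3.4 names three potential drug-related risks, "one related to liver function test changes seen with F6". Sections 1.3.4 and 4.2.2 then give two liver criteria for interrupting dosing and retesting: GLDH at or above 3x ULN, with no cohort limit, and "Bilirubin \geq 2x ULN together with an INR \geq 1.5x ULN (Cohort 2 and 3 only"). On the choice of marker, 1.3.4 says of ALT and AST that "further elevations in these enzymes due to liver toxicity may be difficult to see" in this disease, and that "GLDH is being evaluated and is considered a more specific liver enzyme marker".

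SAP 9.8.3 states: "The number (%) of subjects who fulfill the following liver function test criteria at any time after the start of dosing will be tabulated". The rows are ALT and AST at 1x, 2x and 3x ULN, total bilirubin at 1x and 2x ULN, alkaline phosphatase at 1.5x ULN, and GLDH at 1x ULN. A separate Hy's Law count follows. Coagulation has its own table: "For Cohort 2 the number (%) of subjects who fulfill the following coagulation test criteria at any time after the start of dosing", with rows for INR at or above 1.5x ULN and aPTT above ULN. Then: "A listing will also present all data that meet these criteria along with the value related to ULN". That sentence names no cohort.

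The same section also gives by-visit summaries, including how many boys are high, low or normal "with respect to their reference range will be tabulated". SAP 5.4.2 confirms that coagulation is sampled in Cohorts 2 and 3.

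**The concern.** A criteria table is where a reader looks to see how many boys reached a level that the protocol treats as actionable. Here the cut-offs in the tables are not the protocol's.

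- **GLDH.** The marker that the protocol regards as more specific gets only a 1x ULN row, while ALT and AST, which it regards as hard to interpret in DMD, are taken up to 3x ULN. Exclusion criterion 4 admits boys with GLDH up to 1.5x ULN, so the 1x row can count a boy whose GLDH never rose on treatment.
- **Joint criterion.** Bilirubin and INR are each counted at the right threshold, but in different tables and each over the whole period. The only combined criterion counted is Hy's Law, which protocol 1.3.3 says is hard to apply in DMD.
- **Cohort 3.** The joint criterion applies there and the samples are taken, yet the coagulation-criteria count is restricted to Cohort 2 without a stated reason.

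Safety is a primary objective. At stake is whether the report shows directly how often its own liver criteria were met.

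**Working it through.** The plan gives no figure to reproduce. The check sets the criteria against the tables and then does some simple counting.

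**1. Criteria against rows**

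| Protocol 1.3.4 and 4.2.2 | Nearest count in SAP 9.8.3 | Counted? |
|---|---|---|
| GLDH ≥3x ULN, all cohorts | GLDH ≥ULN | No |
| Bilirubin ≥2x ULN together with INR ≥1.5x ULN, Cohorts 2 and 3 | Bilirubin ≥2x ULN alone; INR ≥1.5x ULN alone, Cohort 2 only | No |

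Result: 0 of 2. SAP section 10 does not list these tables among the items deferred to a later version, nor does it explain the choice.

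**2. Rows in the liver table.** ALT 3 + AST 3 + bilirubin 2 + alkaline phosphatase 1 + GLDH 1 = 10. Six are ALT or AST and one is GLDH.

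**3. Cohort coverage.** Planned sizes (SAP 3.1) are about 10 in Cohort 2 and about 15 in Cohort 3, so the joint criterion applies to about 10 + 15 = 25 boys. The coagulation-criteria table covers 10/25 = 40% and leaves out 15/25 = 60%. This describes that one table only.

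**4. Can the joint count be read from the separate counts?** If a boys meet the bilirubin cut-off and b meet the INR cut-off among n, the number who meet both lies between max(0, a + b − n) and min(a, b). Assume for illustration a = b = 2 and n = 10: max(0, −6) = 0 and min(2, 2) = 2, so the answer may be 0, 1 or 2. These bounds ignore timing; a boy could meet the two cut-offs on different dates. If either count is zero, the joint count is zero. In Cohort 3 there is no INR count, so the bilirubin count is only an upper bound.

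**5. Can the 1x GLDH row stand in for 3x?** In the earlier F6 study (protocol 1.3.3), 5 of 8 boys exceeded ULN and 1 of 8 exceeded 2x ULN. At most 1 of those 5 could have reached 3x. This gives direction only: dosing there was in 7-day periods with F6.

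**6. How often are bilirubin and INR scheduled together?** From the SAP 5.4.2 table, Day 7 to Week 48:

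- Cohort 2: liver tests at Day 7 and Weeks 4, 8, 12, 24, 36 and 48 = 7 visits; coagulation at Day 7 and Weeks 12, 24, 36 and 48 = 5; 5/7 = 71%.
- Cohort 3: liver tests at Day 7 and Weeks 4, 12, 24, 36 and 48 = 6 visits; coagulation at the same 5; 5/6 = 83%.

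A joint row can therefore be built from scheduled data, with gaps that a footnote should state.

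**The case against.** The best reply is that this is a choice of table layout in a descriptive, unpowered study. Protocol 12.1.4.3 promises only changes from baseline for laboratory data, and neither document says that individual stopping criteria must appear as table rows. The information also exists elsewhere. By-visit summaries give minima and maxima. Any boy with GLDH at or above 3x ULN falls in the GLDH listing, which shows value/ULN. For about 10 boys in Cohort 2, matching two short listings gives the joint count. Discontinuations are tabulated with reasons (SAP 9.2), and temporary and permanent cessations are counted (SAP 9.4.1). The liver risk is tied to F6, which Cohort 3 does not take, and the main study report carries only serious adverse events for Cohort 3 (SAP 7.0).

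All of this is true, and it limits the weight of the point. It does not supply the counts. A by-visit maximum shows an extreme but not how many boys reached it. The cessation and discontinuation tables are not defined by these criteria. The F6 link may explain the Cohort 2 wording, but protocol 4.2.2 still applies the joint criterion to Cohort 3. SAP 7.0 plans later Cohort 3 analyses and a final report, and nothing in the SAP extends the table to them.

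Two further remarks bear on the remedy. Protocol 4.2.2 distinguishes a first qualifying result from one confirmed on repeat, and it gives no time window for the joint criterion. The new rows must therefore state what they count.

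**Conclusion.** The point holds. The SAP criteria tables count neither protocol liver criterion (0 of 2), and the coagulation-criteria count leaves out about 15 of the about 25 boys to whom the joint criterion applies. Those sizes are planned, approximate numbers. The joint-count example is an assumption, and the earlier F6 figures show direction only.

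This is a gap in summary tables. It does not mean that data are lost, that a signal has been missed or that a protocol commitment has been broken. The conclusion rests on the SAP text; the separate list of tables and the monitoring committee's documents were not available. The change should be made because these specific rows and this cohort limit are what the programmers will follow, and correcting them costs very little.

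**What to change.** In SAP 9.8.3:

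1. Add a row for GLDH ≥3x ULN, all cohorts.
2. Add a row for bilirubin ≥2x ULN together with INR ≥1.5x ULN, Cohorts 2 and 3, matched on sample date. Matching on date is a reporting convention proposed here, since the protocol defines no window. Footnote that INR is not scheduled with the liver tests at Weeks 4 and 8 (Cohort 2) and Week 4 (Cohort 3), and that the rows count any qualifying result, whether or not a repeat confirmed it.
3. Include Cohort 3 in the coagulation-criteria table when that cohort is reported, and state that the accompanying listing covers Cohorts 2 and 3.

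The cost is two rows, one footnote and one more cohort in an existing table, all from data already collected. No clinical threshold, stopping rule or sampling schedule is altered.
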